8.2 Assessment of Adverse Events

The PI(s) or designee(s) is (are) responsible for obtaining, assessing, and documenting all AEs during the study.

8.2.1 Collection of Information

Adverse event information will be collected from the time of signature of the ICF at V10 onwards until the end of the extension study for the subject either by the PI(s) or designee(s) via spontaneous reporting or by the use of consistent, open, non-directive questions from study site staff (*e.g.*, “Have you had any health problems since the previous visit/How are you feeling

Confidentiality Statement

Data and information contained in this document are considered to constitute trade secrets and confidential commercial information, and the legal protections provided to such trade secrets and confidential information are hereby claimed under the provisions of applicable law. No part of this document may be publicly disclosed without the written consent of Philip Morris Products S.A.

since you were last asked?”). At the discretion of the PI(s) or designee(s), the collection of AE information may also be triggered from the review of the subject questionnaires and the VAS. However, during the visits, the main source for AE collection will be face-to-face interview(s) with the subject.

Information recorded will include: verbatim description of the AE, start and stop dates and times, seriousness, severity (intensity), action taken (*e.g.*, whether or not the AE led to the subject’s withdrawal from the study), and outcome (*e.g.*, resolved, withdrawal due to AE).

For each AE, the intensity will be graded on a 3-point intensity scale (mild, moderate, severe) using the definitions provided in section 8.2.3.

Any exacerbation/worsening or increased frequency of an AE or pre-existing condition shall be evaluated and recorded.

Correct medical terminology/concepts are preferred when recording AE terms, and abbreviations must be avoided. Wherever possible, a diagnosis is to be used to describe an AE as a diagnosed medical condition rather than individual signs and symptoms (*e.g.*, record “pneumonia” rather than “fever”, “cough”, “pulmonary infiltrate” or “septicemia” rather than “fever” and “hypotension” following blood sample).

Any AE that meets the serious criteria must be recorded both on the AE report form of the CRF and on a separate SAE report form (section 8.3).

8.2.2 Period of Collection

From the time of signature of the ICF of the extension study (at V10) until the end of the study (EOS), all AEs (includes SAEs) will be collected by the study site staff as described below. Any AE ongoing at V10 will be followed up during the extension study.

8.2.2.1 From Enrollment until the End of the Study

Any new, clinically relevant, abnormal finding or worsening of a pre-existing condition/concomitant disease detected during the study including the safety follow-up period will be documented as an AE and/or SAE.

During the safety follow-up period spontaneously reported AEs and/or SAEs will be recorded in the CRF. Any AEs/SAEs ongoing during the 28 day safety period will be actively followed up by the PI(s) or designee(s) until they have been resolved, stabilized (*i.e.*, no worsening of condition), or until an acceptable explanation has been found.

Upon/after the end of the safety follow-up period for all ongoing AEs, the PI(s) will refer the subject to his General Practitioner for follow up of those AEs (section 8.3) until they have been resolved, stabilized (*i.e.*, no worsening of condition), or until an acceptable explanation has been found. All ongoing SAEs at the end of the study will be followed up by the PI(s).

Confidentiality Statement

Data and information contained in this document are considered to constitute trade secrets and confidential commercial information, and the legal protections provided to such trade secrets and confidential information are hereby claimed under the provisions of applicable law. No part of this document may be publicly disclosed without the written consent of Philip Morris Products S.A.

8.2.3 Intensity of Adverse Event

For each AE, the intensity will be graded by the PI(s) on a 3-point intensity scale (mild, moderate, severe) using the following definitions:

- Mild:** The AE is easily tolerated and does not interfere with daily activity.
- Moderate:** The AE interferes with daily activity, but the subject is still able to function.
- Severe:** The AE is incapacitating and requires medical intervention.

According to CIOMS (Council for International Organizations of Medical Sciences) VI Working group, changes in severity (Intensity) and maximum intensity of AEs must be documented.

8.2.4 Relationship to Investigational Product and Relationship to Study Procedures

It is difficult to establish a firm method to distinguish an adverse reaction (that is AE that is causally related to the IP) from a clinical adverse event that is temporally associated to the use of an IP.

In general, all AEs and/or SAEs will be assessed by the PI(s) or designee(s) as either “related” or “not related” to IP as described below. In addition to the assessment of the relationship of the clinical event to the IP, the PI(s) or designee(s) shall document a potential relationship of the clinical event to any particular study procedure.

Not related: The temporal relationship of the clinical event to IP administration makes a causal relationship unlikely, or, concomitant medication, therapeutic interventions, or underlying conditions provide a sufficient explanation for the observed event.

Related: The temporal relationship of the clinical event to study IP administration makes a causal relationship possible, and concomitant medication, therapeutic interventions, or underlying conditions do not provide a sufficient explanation for the observed event.

8.2.5 Expectedness

Any AE assessed as related to the IP will be assessed for its expectedness. An AE will be regarded as “unexpected” if its nature or severity is not consistent with information already known about the IP, and is not listed in the current IB. The IB provides further detail on signs or symptoms that might be expected with the use of the IP, including information relating to device malfunction or misuse.

Confidentiality Statement

Data and information contained in this document are considered to constitute trade secrets and confidential commercial information, and the legal protections provided to such trade secrets and confidential information are hereby claimed under the provisions of applicable law. No part of this document may be publicly disclosed without the written consent of Philip Morris Products S.A.

8.3 Reporting and Follow-Up of Serious Adverse Events

Any SAEs reported or observed during the study whether or not attributable to the IP, or to any study procedures, or any SAE related to the product and spontaneously reported after the safety follow-up must be reported by the Principal Investigator or designee **within 24 hours after first awareness by any party involved in the study to** [REDACTED] and to the Sponsor.

An SAE report form must be faxed or e-mailed as an attachment to:

[REDACTED] [REDACTED] **Fax number:** [REDACTED]
E-mail: [REDACTED]
Address: [REDACTED]
[REDACTED]
[REDACTED]
[REDACTED]
Sponsor Contact: **Phone:** [REDACTED]
[REDACTED] MD
Medical Safety Officer
E-mail 1: [REDACTED]@pmi.com
E-mail 2: [REDACTED]@pmi.com

The PI(s) or designee(s) is (are) responsible for local reporting (*e.g.*, to the IRB) of SAEs that occur during the study, according to local regulations.

Any SAE will be reported by the Sponsor to the FDA Center for Tobacco Products Office of Science within 15 business days after the report is received by the Sponsor.

Any additional/follow-up information that becomes available after the initial SAE report form has been completed will be forwarded to [REDACTED] [REDACTED] and the Sponsor within 24 hours after first awareness by any person at the site using a follow-up to the existing SAE report form.

The follow-up SAE report form must include the minimum information required as described in the safety management plan (SMP) for form completion and only changed/new information needs to be specified. Information provided in the follow-up SAE report form supersedes any information that was initially reported.

All SAEs will be followed up by the PI(s) or designee(s) and/or [REDACTED] until their resolution or until the PI(s) or designee(s) consider(s) the event to be stabilized (*i.e.*, no

Confidentiality Statement

Data and information contained in this document are considered to constitute trade secrets and confidential commercial information, and the legal protections provided to such trade secrets and confidential information are hereby claimed under the provisions of applicable law. No part of this document may be publicly disclosed without the written consent of Philip Morris Products S.A.

worsening of condition), or an acceptable explanation has been found (*e.g.*, a chronic condition).

The SAE report form to be used in this study is provided as a separate document and included in the Investigator site file. All SAEs will be recorded, in addition to the SAE report form.

8.4 Reporting of Other Events Critical to Safety Evaluations

8.4.1 Abnormal Results of Laboratory Tests

Any clinical safety laboratory test result that is outside of the normal reference range will be reviewed by the PI(s) or designee(s) and assessed for clinical relevance. If the subject is enrolled in the extension study and, if the abnormal laboratory result is detected after signature of the extension study ICF at V10 onwards, and is considered clinically relevant (see below), this should be recorded as an AE in the CRF of the extension study. If the subject is not enrolled (*e.g.* screen failure), the AE should be recorded in the CRF of the original study.

The grading scheme described in the Common Terminology Criteria for Adverse Events and Common Toxicity Criteria [CTCAE] version 4.03 (Appendix 5) will be used by the PI(s) or designee(s) to assess abnormal laboratory AEs as follows:

- All Grade 1 abnormal laboratory values will be evaluated by the PI(s) or designee(s) with respect to Baseline value (V3 of the original study) and clinical relevance. If considered to be clinically relevant the Investigator or designee must report it as an AE. All Grade 2 and higher abnormal laboratory values must be reported as, or linked to, an AE/concomitant disease.
- If there is any worsening in grade from Grade 2 and above during the study the PI(s) or designee(s) must report this worsening as an AE.
- Where there is no grading available, the abnormal laboratory value will be evaluated by the PI(s) or designee(s) and assessed for clinical relevance. If considered to be clinically relevant, the PI(s) or designee(s) will report it as an AE.
- Any other abnormal clinical laboratory result (including those that are not part of the core safety assessments) can, at the discretion of the PI(s) or designee(s), be reviewed and assessed. Even if they do not meet the criteria of the CTCAE grading scheme (please see above), the PI(s) or designee(s) may consider them to be of clinical relevance and, if they are, must report them as AEs.
- In general, laboratory values will be recorded as ‘increased <lab parameter>’ or ‘decreased <lab parameter>’ to ensure consistency of recording/coding.

All other information (*e.g.*, relationship to IP, intensity, seriousness, outcome) will be assessed as for other AEs.

Confidentiality Statement

8.5 Reporting and Follow-Up of Pregnancies

For pregnancies detected at V10, subject will not be offered to enter in the extension study. A pregnancy form will be filled during V10 as part of the original study assessments. The diagnosed pregnancy will be captured in the CRF of the original study only, and not in the CRF of the extension study, as it will be considered as an event from the original study.

Any pregnancy having occurred after enrollment in the extension study, potentially associated with exposure to the IP, including pregnancies spontaneously reported to the PI(s) or designee(s) after the EOS must be reported by the PI(s) or designee(s) and followed up until the pregnancy outcome is reached. Potentially associated with exposure to the IP is defined as the pregnancy where a conception date being calculated as the date after first exposure and before the last exposure to the IP. In case the conception occurs before the enrollment in the extension study but the pregnancy test is negative at V10, the occurrence of the pregnancy will be captured in the CRF of the extension study only once the pregnancy is diagnosed.

The PI(s) or designee(s) will complete a pregnancy form (provided as a separate document) for all pregnancies diagnosed after enrollment in the extension study (including positive urine pregnancy tests).

The procedure to report a pregnancy and provide any additional/follow-up information to [REDACTED] and the Sponsor must be followed in the same manner and within the same timelines as described for an SAE (section 8.3). No invasive study procedures, including drawing of blood must be done in such subjects after the discovery of pregnancy.

[REDACTED] will follow up pregnancies until an outcome is reached (*e.g.* normal delivery, spontaneous abortion or voluntary termination). Any pregnancy complication, adverse pregnancy outcome or maternal complications will be recorded.

The PI(s) or designee(s) is(are) responsible for informing the IRB of any pregnancy that occurs during the study and its outcome, according to local regulations.

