5.2 Discontinuation of Subjects from the Study

Discontinued subjects will include both subjects who withdraw from the study (subject's decision) or subjects who are removed from the study. A subject can only be discontinued from the study after enrollment.

Subjects will be informed that they are free to withdraw from the study (upon decision of the subject) at any time. Subjects should be questioned for the reason for withdrawal from the study, although they are not obliged to disclose it. If the subject withdraws from the study he/she will be asked to confirm at least the following points and this information will be fully documented by the PI(s) or designee(s):

- If applicable, the subject still consents for long-term biobanking (2 ICFs).
- Whether the subject requested withdrawal of Health Insurance Portability and Accountability Act (HIPAA) authorization.
- The subject agrees to undertake the early termination procedures (section 9.4).

When a subject is discontinued from the study, early termination procedures (section 9.4) are performed within a period of 5 days after the discontinuation date unless the subject refuses to perform the assessments. After the date of early termination visit, the subject will enter into

Confidentiality Statement

Data and information contained in this document are considered to constitute trade secrets and confidential commercial information, and the legal protections provided to such trade secrets and confidential information are hereby claimed under the provisions of applicable law. No part of this document may be publicly disclosed without the written consent of Philip Morris Products S.A.

the 28 day safety follow-up period. In case an early termination visit is not performed, the subject will still enter into the 28 days Safety Follow-up period after the discontinuation date.

Subjects must be discontinued from the study for any of the following reasons:

- Withdrawal of informed consent.
- Any AE or condition (including clinically relevant changes in a laboratory parameter), which at the discretion of the PI(s) or designee(s) no longer justifies the subject's participation in this study.
- Positive pregnancy testing (section 8.5).

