7.5.1 Clinical Chemistry, Hematology, and Urine Analysis for the Safety Panel

Hematology, clinical chemistry and urine analysis for the safety panel will be measured according to Appendix 1.

Blood samples will be taken after at least 10 hours of fasting (section 6.6.2). The urine test will be performed semi-quantitatively as a urine test. Parameters to be measured are listed in Table 3. Total count of WBC will be evaluated in blood as part of the “smokers’ health profile.”

Table 3 Clinical Laboratory Parameters for Safety Panel

| Hematology | Clinical Chemistry | Urine analysis |
|--|---|---|
| 
• Hematocrit• Hemoglobin• Mean corpuscular hemoglobin (MCH)• Mean corpuscular hemoglobin concentration (MCHC)• Mean corpuscular volume (MCV)• Platelet count• Red blood cell (RBC) count*• White blood cell (WBC) count*• Differential WBC count:
- Neutrophils- Basophils- Eosinophils- Lymphocytes- Monocytes | 
• Albumin• Total protein• Alkaline phosphatase (AP)• Alanine aminotransferase (ALT)• Aspartate aminotransferase (AST)• Blood urea nitrogen (BUN)• Creatinine• Gamma-glutamyl transferase (GGT)• Glucose• Lactate dehydrogenase (LDH)• Potassium• Sodium• Total bilirubin• Direct bilirubin• Total cholesterol (TC)• Triglycerides (TG) | 
• pH• Bilirubin• Glucose• Nitrite• Red blood cell traces• Protein• Specific gravity |

*RBC and WBC morphology tests might be performed in case of abnormal values.

Confidentiality Statement

Data and information contained in this document are considered to constitute trade secrets and confidential commercial information, and the legal protections provided to such trade secrets and confidential information are hereby claimed under the provisions of applicable law. No part of this document may be publicly disclosed without the written consent of Philip Morris Products S.A.

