7.5.2 Urine Pregnancy Testing

A pregnancy test will be done on all female subjects according to Appendix 1.

Female subjects with a positive pregnancy test at V10 will not be offered to enter in the extension study and the PI(s) or designee(s) will inform those subject about the risks associated with smoking during pregnancy. All pregnancies detected during the study must be reported and handled as described in section 8.5.

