9.2 Extended Exposure Period

Table 5 shows the assessments that will be performed at V11, V12, V13, V14, and V15:

Table 5 Time Schedule – V11 (Week 30), V12 (Week 35), V13 (Week 39), V14 (Week 43), V15 (Week 48)

| Time | Blood Sample | Procedures | Additional Information |
|---------------------------|--------------|------------------------------------|--|
| Start of Procedure | | V11, V12, V13, V14, and V15 | |
| Start of the visit | | Check-in at site | Product use will be allowed on site in the THS 2.2 and CC arms |

Confidentiality Statement

Data and information contained in this document are considered to constitute trade secrets and confidential commercial information, and the legal protections provided to such trade secrets and confidential information are hereby claimed under the provisions of applicable law. No part of this document may be publicly disclosed without the written consent of Philip Morris Products S.A.

| Time | Blood Sample | Procedures | Additional Information |
|---------------------------|---------------------|--|---|
| Start of Procedure | | V11, V12, V13, V14, and V15 | |
| | | | The use of THS 2.2 in subjects randomized to CC will be forbidden |
| During the visit | | Return of unused and partially used packs of THS Tobacco Sticks by the subject randomized to THS 2.2 arm | |
| During the visit | | Urine pregnancy test (females only) | |
| During the visit | | AE/SAE questioning; Concomitant medication | At any time during the day |
| During the visit | | Weight and calculation of BMI | At V13 only |
| During the visit | | Vital signs (blood pressure, pulse rate, respiratory rate) | After resting for at least 5 minutes in supine position At any time during the day |
| During the visit | | Information on the risk of smoking/smoking cessation advice and debriefing on THS 2.2 | |
| During the visit | | Dispensing of THS 2.2 | THS 2.2 arm only |
| During the visit | | Distribution of the 24-hour urine containers | At V15 only |
| End of the visit | | Check-out from site | |

Abbreviations:

AE = Adverse event; CC = Conventional cigarette(s); SAE = Serious adverse event; THS = Tobacco Heating System.

Confidentiality Statement

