9.4 Early Termination Procedures

The following early termination procedures will be performed within 5 days of the date of study discontinuation, if a subject is discontinued from the study:

- AE/SAE recording.
- Clinical laboratory parameters (hematology, clinical chemistry, and urine safety analysis).
- Physical examination.
- Lung function (spirometry pre-bronchodilator and spirometry post-bronchodilator). In case the value of the test(s) do not meet the criteria the subject will need to come back within a 7 day window to repeat the test(s).
- Urine pregnancy.
- Vital signs.
- ECG.
- Information on the risk of smoking, smoking cessation advice, and debriefing on THS 2.2.

If the early termination visit occurs on the same day than a planned visit (e.g. the subject wants to withdraw or is discontinued in the middle of V12), all assessments that have been performed during the planned visit should not be conducted again for the ET procedures. In case an early

Confidentiality Statement

Data and information contained in this document are considered to constitute trade secrets and confidential commercial information, and the legal protections provided to such trade secrets and confidential information are hereby claimed under the provisions of applicable law. No part of this document may be publicly disclosed without the written consent of Philip Morris Products S.A.

termination visit is not performed, the subject will still enter into the 28 days Safety Follow-up Period after the discontinuation date.

Confidentiality Statement

Data and information contained in this document are considered to constitute trade secrets and confidential commercial information, and the legal protections provided to such trade secrets and confidential information are hereby claimed under the provisions of applicable law. No part of this document may be publicly disclosed without the written consent of Philip Morris Products S.A.

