Hematology: hematocrit, hemoglobin, mean corpuscular hemoglobin, mean corpuscular hemoglobin concentration, mean corpuscular volume, platelet count, red blood cell count, white blood cell count, differential white blood cell count. Platelet count, white blood cell count from hematology will be evaluated as clinical risk endpoints. **Urine analysis:** pH, bilirubin, glucose, nitrite, red blood cell traces, protein, specific gravity. **Clinical chemistry:** albumin, total protein, alkaline phosphatase, alanine aminotransferase, aspartate aminotransferase, blood urea nitrogen, creatinine, gamma-glutamyl transferase, glucose, lactate dehydrogenase, potassium, sodium, total bilirubin, direct bilirubin, total cholesterol, triglycerides. White blood cell count (WBC) will also be evaluated as part of the “smokers’ health profile”.

^b Systolic and diastolic blood pressure, pulse rate, and respiratory rate. Vital signs will be assessed after at least 5 minutes in supine position.

^c Height will be transferred from the original study

Confidentiality Statement

Data and information contained in this document are considered to constitute trade secrets and confidential commercial information, and the legal protections provided to such trade secrets and confidential information are hereby claimed under the provisions of applicable law. No part of this document may be publicly disclosed without the written consent of Philip Morris Products S.A.

- d CO breath test: the test will be conducted once and should be done in conjunction with COHb blood where applicable.
- c Lung function assessments must be performed in the following sequence:
 - Pre-bronchodilator spirometry testing.
 - Pre-bronchodilator lung volume using helium dilution (only at V10 and V16).
 - Post-bronchodilator spirometry testing.
- f Use of any tobacco/nicotine containing products will be captured in the ed diary.
- g Early termination procedures will be conducted in subjects who terminate from the study earlier.
- h At V16, only subjects in the THS 2.2 arm will answer to the ITUQ.
- i During the safety follow-up period, spontaneous reporting of new AEs/SAEs by the subject will be done.
- j Once at every visit. Samples will only be taken if additional ICF for sample biobanking is signed by the subject.

All assessments done at V10 in the context of the original study do not need to be repeated for the extension study.

Confidentiality Statement

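### The early termination list in Protocol 9.4 has no pregnancy exception, so it calls for blood samples that Protocol 8.5 forbids, mainly after a positive test at V11 to V15

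*Protocol*

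**What the plan says.** Protocol 8.5 is unconditional about a subject who is found to be pregnant after enrollment: "No invasive study procedures, including drawing of blood must be done in such subjects after the discovery of pregnancy".

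Protocol 5.2 lists the reasons for which discontinuation is compulsory, and one of them is "Positive pregnancy testing (section 8.5"). The same section sends a discontinued subject to the 9.4 procedures within 5 days, "unless the subject refuses to perform the assessments". No other exception is given.

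Protocol 9.4 applies its list to any discontinued subject, whatever the reason. The list includes "Clinical laboratory parameters (hematology, clinical chemistry, and urine safety analysis"). It does not mention 8.5. The footnote to the schedule in Appendix 1 is equally general: "Early termination procedures will be conducted in subjects who terminate from the study earlier".

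Protocol 7.5.1 confirms that the panel needs blood: "Blood samples will be taken after at least 10 hours of fasting (section 6.6.2").

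Protocol 7.5.2 points the other way, towards 8.5: "All pregnancies detected during the study must be reported and handled as described in section 8.5".

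**The concern.** Read literally, 5.2 and 9.4 call for a blood sample within 5 days from a subject from whom 8.5 says no blood may be taken. Staff running an exit visit are likely to work from the 9.4 list, and nothing in it tells them to leave the blood out. The stake is the protection of a pregnant subject, together with a foreseeable protocol deviation whichever section the site follows. Efficacy inference is not at stake.

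**Working it through.** No formula decides this point. The check is to follow one subject through the sections.

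1. **Trigger.** Tables 5 and 6 and Appendix 1 schedule "Urine pregnancy test (females only") at V11, V12, V13, V14, V15 and V16, which is 6 visits. A positive result means discontinuation under 5.2.

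2. **Route.** Section 5.2 then leads to 9.4 within 5 days, with refusal as the only way out.

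3. **Content of 9.4.** The items are AE/SAE recording, clinical laboratory, physical examination, lung function, urine pregnancy test, vital signs, ECG, and risk information with debriefing. That makes 8, of which 1 (clinical laboratory) needs blood. The pregnancy test is listed after the laboratory item, and nothing links the two.

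4. **What would be drawn without 9.4.**
   - At V11 to V15, Table 5 marks no row as a blood sample. At these 5 of the 6 visits the draw arises only because discontinuation brings in the 9.4 list. The clause in 9.4 that spares assessments already done at a same-day visit does not help, because no blood has been taken.
   - At V16, Table 6 marks 6 rows as blood samples: clinical laboratory, clinical risk endpoints, two biobanking rows that need consent, nicotine/cotinine, and COHb. The pregnancy test row stands before all 6. The printed order therefore supports 8.5, but no row says to stop if the test is positive.

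5. **Where the values would go.** Take SAP Table 17 for nominal study days, the ± 5 day visit window and the 5-day limit for early termination. Assume that discontinuation is dated on the day of the positive test.
   - V11 to V15: earliest 211 − 5 = day 206; latest 337 + 5 + 5 = day 347. Both lie within Months 7 to 11 (days 198 to 351), where no hematology or chemistry is scheduled. Under SAP 12.1.6 these values would not be combined into the visit summaries. A WBC from such a draw would not reach the primary model, which uses V7, V10 and V16.
   - V16: earliest 365 − 5 = day 360; latest 365 + 5 + 5 = day 375. Both fall in Month 12 (day 352 or later), where the panel is scheduled. Four of the 8 primary endpoints come from V16 blood (HDL-C, WBC, sICAM-1, COHb). For a subject who tests positive before the draw, 8.5 already rules them out.
   - A Grade 2 or higher exit value would have to be reported as, or linked to, an AE or concomitant disease (Protocol 8.4.1). Entry into the worst-grade shift tables is doubtful. SAP 12.7.4.2.4 limits them to the randomized exposure period, which SAP 4.1.1 ends at the discontinuation date, although SAP 12.7.4.3 speaks more widely of grades after Baseline.

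**The case against.** The strongest reply is that the protocol has already settled the matter. Section 8.5 is specific and absolute, 9.4 is a general list, and the site is pointed to 8.5 by the pregnancy reason in 5.2 and again by 7.5.2. A careful reader would let 8.5 prevail. Site procedures or the laboratory manual, which are not available here, may also say so. Most of this stands: the intent is not in doubt, and this is an internal inconsistency rather than an open question. It does not put the exception where staff act. The pointer in 5.2 is attached to the reason for discontinuation. The sentence in 5.2 that sends subjects to early termination carries its own exception, and that exception is refusal, not pregnancy. The protocol does write pregnancy conditions into its visit tables elsewhere: Table 4 makes the extension offer depend on a negative test.

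Three stronger readings are tempting, and the documents do not support them.

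- A reader might infer that every discontinued subject must give blood. Refusal is allowed.
- A reader might infer that Table 6 directs a site to take the full V16 volume, around 80 mL at most under 7.6.1, from a woman who has just tested positive. The test comes first and a positive result triggers discontinuation, so the full V16 set is not clearly what applies. That maximum also includes 10 + 9 = 19 mL of optional biobanking. The nearest figure to the safety panel is 13 mL for safety and repeated analysis at V16; no volume is given for early termination.
- A reader might infer that the results are at risk. Step 5 of the working shows why they are not.

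**Conclusion.** The conflict is in the current text and should be corrected. It concerns 1 of 8 early termination items. It bites mainly at V11 to V15, where the 9.4 list alone generates a draw that 8.5 forbids; at V16 only a stop note is missing. The documents give no proportion of women and no expected pregnancy rate, so the number of cases cannot be calculated. Because agreement to effective contraception is an entry requirement, few are expected. The primary analysis is essentially unaffected. The conclusion rests on reading 5.2 and 9.4 as written and on a site using the 9.4 list for the exit visit.

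**What to change.** Add one sentence to 9.4: once pregnancy is known, no blood is drawn and no other invasive study procedure is done, per 8.5, and the urine pregnancy test is read before any early termination blood draw. Put a short cross-reference beside the early termination rule in 5.2 and a stop note in Table 6. Reading the test first is a sensible safeguard rather than the repair of an error, since 8.5 applies only once pregnancy has been discovered.

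The amendment should not say that all remaining procedures are still done. The 9.4 list includes post-bronchodilator spirometry, which means about 400 µg of salbutamol (7.3.5.1), and 2.3.2 names the bronchodilator as a foreseeable procedural risk. Whether to do that test in a subject known to be pregnant should be left to the investigator's judgment.

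The cost is a short amendment or site memo and a few lost exit safety laboratory values. Section 8.5 already forbids collecting these, so nothing that the protocol permits is given up.
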